5.2.5. Definition of start of new anti-cancer drug therapy

Start date of new anti-cancer drug therapy is used to determine the end of the on-treatment period (see Section 5.2.7).

The start date of new anti-cancer drug therapy is the earliest start date of anti-cancer drug therapy recorded in the 'Follow-up Cancer Therapy' eCRF pages that is after the first dose of study treatment. When the start date of anti-cancer drug therapy is missing or partially missing, the imputation rules described in Section 5.3.3.4 should be applied using only data from the 'Follow-up Cancer Therapy' eCRF pages.

5.2.6. Definition of start of new anti-cancer therapy

Start date of new anti-cancer therapy (drug, radiation, surgery) is used for censoring in efficacy analyses (see Section 6.1.1 and Section 6.2.2).

The start date of new anti-cancer therapy is the earliest date after randomization amongst the following:

- Start date of anti-cancer drug therapy recorded in the 'Follow-up Cancer Therapy' eCRF pages
- Start date of radiation therapy recorded in 'Concomitant Radiation Therapy', and 'Follow-up Radiation Therapy' eCRF pages with 'Treatment Intent' = 'Curative in intent'
- Surgery date recorded in 'Concomitant Surgery', and 'Follow-up Surgery' eCRF pages when 'Surgery Outcome' = 'Resected' or 'Partially Resected'.

When start date of anti-cancer therapy is missing or partially missing, the imputation rules described in Section 5.3.3.4 should be applied using ‘Follow-up Cancer Therapy’, ‘Concomitant Radiation Therapy’, ‘Follow-up Radiation Therapy’, ‘Concomitant Surgery’, and ‘Follow-up Surgery’ eCRF pages.

5.2.7. Definition of on-treatment period

Safety endpoints will be summarized based on the on-treatment period unless otherwise specified.

On-treatment period is defined as the time from the first dose of study treatment through minimum (30 days + last dose of study treatment, start day of new anti-cancer drug therapy – 1 day).

Safety data collected outside the on-treatment period as described above will be listed and flagged in listings but will not be summarized.

5.2.8. Standard derivations and reporting conventions

The following conversion factors will be used to convert days into weeks, months or years: 1 week = 7 days, 1 month = 30.4375 days, 1 year = 365.25 days.

Demographics and physical measurements:

- Age [years]:
 - (date of given informed consent - date of birth + 1) / 365.25
 - In case of missing day, day only: Age [years]: (year/month of given informed consent – year/month of birth)
 - In case only year of birth is given: Age [years]: (year of given informed consent - year of birth)

The integer part of the calculated age will be used for reporting purposes.

- $BMI (kg/m^2) = weight (kg) / [height (m)]^2$

For reporting conventions, mean and median should generally be displayed to one more decimal place than the raw data and standard deviation should be displayed to two more decimal places than the raw data. Percentages will be reported to one decimal place. The rounding will be performed to closest integer / first decimal using the common mid-point between the two consecutive values. E.g., 5.1 to 5.4 will be rounded to an integer of 5, and 5.5 to 5.9 will be rounded to an integer of 6.

5.2.9. Unscheduled visits

Generally, data collected at unscheduled visits will be included and analyzed for both safety and efficacy analyses in the same fashion as the data collected at scheduled visits except where otherwise noted in the sections that follow. Descriptive statistics (mean, SD, median,

minimum, maximum, quartiles) by nominal visit or time point for safety endpoints such as laboratory measurements, ECGs and vital signs will include only data from scheduled visits.

5.2.10. Adequate baseline tumor assessment

Adequate baseline is defined using the following criteria:

- All baseline assessments must be within 28 days prior to and including the date of randomization.
- All documented lesions must have non-missing assessments (i.e. non-missing measurements for target lesions and non-missing lesions assessment status at baseline for non-target lesions).

5.2.11. Adequate post-baseline tumor assessment

An adequate post-baseline assessment is defined as an assessment where a response of CR, PR, SD, non-CR/non-PD, or PD can be determined (see Section 6.2.2.5). Time points where the response is not evaluable (NE) or no assessment was performed will not be used for determining the censoring date.

5.3. Methods to Manage Missing Data

5.3.1. Missing data

Unless otherwise specified, all data will be evaluated as observed, and no imputation method for missing values will be used.

In all patient data listings imputed values will be presented. In all listings imputed information will be flagged.

Missing statistics, e.g. when they cannot be calculated, should be presented as 'ND' or 'NA'. For example, if N=1, the measure of variability (SD) cannot be computed and should be presented as 'ND' or 'NA'.

5.3.1.1. Pharmacokinetic concentrations

Concentrations Below the Limit of Quantification

For all calculations, figures and estimation of individual pharmacokinetic parameters, all concentrations assayed as below the level of quantification (BLQ) will be set to zero. In log-linear plots these values will not be represented. The BLQ values will be excluded from calculations of geometric means and their CIs. A statement similar to 'All values reported as BLQ have been replaced with zero' should be included as a footnote to the appropriate tables and figures.

Deviations, Missing Concentrations and Anomalous Values

In summary tables and plots of median profiles, concentrations will be set to missing if one of the following cases is true:

1. A concentration has been reported as ND (i.e., not done) or NS (i.e., no sample);

2. A deviation in sampling time is of sufficient concern or a concentration has been flagged as anomalous by the clinical pharmacologist.

Summary statistics will not be presented at a particular time point if more than 50% of the data are missing. For analysis of pharmacokinetic concentrations, no values will be imputed for missing data.

5.3.1.2. Pharmacokinetic parameters

Whether actual or nominal PK sampling time will be used for the derivation of PK parameters will be determined by the results of interim PK analyses. If a PK parameter cannot be derived from a patient's concentration data, the parameter will be coded as NC (i.e., not calculated). NC values will not be generated beyond the day that a patient discontinues.

In summary tables, statistics will be calculated by setting NC values to missing. Statistics will not be presented for a particular treatment if more than 50% of the data are NC. For statistical analyses (i.e., analysis of variance), PK parameters coded as NC will also be set to missing.

If an individual patient has a known biased estimate of a PK parameter (due for example to a deviation from the assigned dose level), this will be footnoted in summary tables and will not be included in the calculation of summary statistics or statistical analyses.

5.3.2. Handling of incomplete dates

5.3.2.1. Disease history

Incomplete dates for disease history (e.g., initial diagnosis date, date of documented, locally advanced, inoperable or metastatic disease diagnosis, date of response or progression in prior treatment) will be imputed as follows:

- If the day is missing, it will be imputed to the 15th day of the month.
- If both day and month are missing and the year is prior to the year of the first study treatment, the month and day will be imputed as July 1st.
- If both day and month are missing and the year is same as the year of the first study treatment, the month and day will be imputed as January 1st.
- If the date is completely missing, no imputation will be performed.

5.3.2.2. Adverse events

Incomplete AE-related dates will be imputed as follows:

- If the AE onset date is missing completely, then the onset date will be replaced by the start of study treatment.
- If only the day part of the AE onset date is missing, but the month and year are equal to the start of study treatment, then the AE onset date will be replaced by the start of study

treatment. For example, if the AE onset date is --/JAN/2015, and study treatment start date is 15/JAN/2015, then the imputed AE onset date will be 15/JAN/2015.

- If both the day and month of the AE onset date are missing but the onset year is equal to the start of study treatment, then the onset date will be replaced by the start of study treatment. For example, if AE onset date is --/--/2014, and study treatment start date is 19/NOV/2014, then the imputed AE onset date will be 19/NOV/2014.
- In all other cases the missing onset day or missing onset month will be replaced by 1.
- Incomplete stop date will be replaced by the last day of the month (if day is missing only), if not resulting in a date later than the date of patient's death. In the latter case the date of death will be used to impute the incomplete stop date.
- In all other cases the incomplete stop date will not be imputed. If stop date of AE is after the date of cut-off outcome of AE is ongoing at cut-off.

5.3.2.3. Prior and concomitant medications

Incomplete prior/concomitant medication dates will be imputed as follows:

- If the medication date is missing completely, then the medication date will be replaced by the start of study treatment.
- If the day of medication date is missing, but the month and year are equal to the start of study treatment, then the medication date will be replaced by the start of study treatment. For example, if the medication start date is --/JAN/2015, and study treatment start date is 15/JAN/2015, then the imputed medication start date will be 15/JAN/2015.
- If both the day and month of medication start date are missing but the start year is equal to the start of study treatment, then the medication date will be replaced by the start of study treatment. For example, if the medication start date is --/--/2014, and study treatment start date is 19/NOV/2014, then the imputed medication start date will be 19/NOV/2014.
- In all other cases the missing medication day or missing medication month will be replaced by 1.
- Incomplete stop date will be replaced by the last day of the month (if day is missing only), if not resulting in a date later than the date of patient's death. In the latter case the date of death will be used to impute the incomplete stop date.
- In all other cases the incomplete medication stop date will not be imputed.

5.3.2.4. Exposure

No imputation will be done for first dose date. Date of last dose of study drug, if unknown or partially unknown, will be imputed as follows:

- If the last date of study drug is completely missing and there is no End of Treatment eCRF page and no death date, the patient should be considered to be ongoing and use the cut-off date for the analysis as the last dosing date
- If the last date of study drug is completely or partially missing and there is EITHER an End of Treatment eCRF page OR a death date available (within the cut-off date), then imputed last dose date is:
 - = 31DECYYYY, if only Year is available and Year < Year of min (EOT date, death date)
 - = Last day of the month, if both Year and Month are available and Year = Year of min (EOT date, death date) and Month < the month of min (EOT date, death date)
 - = min (EOT date, death date), for all other cases

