 YYYY = Year of min [max(PD date + 1, last dose of study treatment + 1), end date of new anti-cancer therapy], AND
 MMM = Month of min [max(PD date + 1 day, last dose of study treatment + 1 day), end date of new anti-cancer therapy]
THEN
 imputed start date = min [max(PD date + 1 day, last dose of study treatment + 1 day), end date of new anti-cancer therapy];
ELSE IF
 YYYY = Year of min [max(PD date + 1, last dose of study treatment + 1), end date of new anti-cancer therapy], AND
 MMM > Month of min [max(PD date + 1 day, last dose of study treatment + 1 day), end date of new anti-cancer therapy]

THEN

imputed start date = 01 MMM YYYY;

ELSE IF

YYYY < Year of min [max(PD date + 1, last dose of study treatment + 1), end date of new anti-cancer therapy]

THEN

imputed start date = DAY (Last day of MMM) MMM YYYY;

ELSE IF

YYYY > Year of min [max(PD date + 1, last dose of study treatment + 1), end date of new anti-cancer therapy]

THEN

imputed start date = 01 MMM YYYY.

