6.6.2. Deaths

The frequency (number and percentage) of patients in the safety analysis set who died and who died within 30 days after last dose of study treatment as well as the reason for death, will be tabulated based on information from the 'Notice of Death' and 'Survival Follow-Up' eCRFs, by treatment arm.

- All deaths
- Deaths within 30 days after last dose of study treatment
- Reason for Death
 - Disease progression
 - Study treatment toxicity
 - AE not related to study treatment
 - Unknown
 - Other.

In addition, date and cause of death will be provided in individual patient data listing together with selected dosing information (study treatment received, date of first / last administration, dose) and will include the following information:

- AEs with fatal outcome (list preferred terms of AEs with outcome=Fatal, as well as AEs of Grade 5),
- Flag for death within 30 days of last dose of study treatment.

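### The last-dose imputation has no branch for a known month in a year before EOT or death, so such a date is moved outside the month the site recorded (minor)

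*SAP*

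**What the plan says.** SAP 5.3.2.4 applies when the last-dose date is partly or wholly missing and an EOT page or a death date exists. Its three branches are:

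1. Year only: "31DECYYYY, if only Year is available and Year < Year of min (EOT date, death date").
2. Year and month: "Last day of the month, if both Year and Month are available and Year = Year of min (EOT date, death date"), provided the recorded month is also earlier.
3. Everything else: "min (EOT date, death date), for all other cases".

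SAP 5.3.3.4 deals with the same kind of partial date for the start of new anti-cancer therapy. When month and year are known it also treats the case "YYYY < Year of min [max(PD date + 1, last dose of study treatment + 1), end date of new anti-cancer therapy"], and the result there is "imputed start date = DAY (Last day of MMM) MMM YYYY".

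The last-dose date is then used in several places:

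- exposure (SAP 6.5.3.1 to 6.5.3.3);
- the on-treatment period, which ends at "minimum (30 days + last dose of study treatment, start day of new anti-cancer drug therapy" minus one day) (SAP 5.2.7);
- the 90-day irAE window (SAP Appendix 1);
- the table line "Deaths within 30 days after last dose of study treatment" (SAP 6.6.2).

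For Arm A, SAP 3.4.1 takes the later of the two drugs' last doses as the last dose of study treatment.

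**The concern.** A last dose with known month and year, in a calendar year before the earlier of EOT and death, meets neither specific branch. Branch 1 requires that only the year is known, and branch 2 requires equal years. The catch-all then replaces the recorded month with the EOT or death date.

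The rule also becomes less accurate when it is given more information, because a bare year stays within that year while a month plus the same year does not. Nothing in the SAP explains why the turn of the year should matter. With 5.3.3.4 handling the same situation explicitly, this reads as an omission and not as a choice.

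What is at stake is mainly descriptive: duration of exposure, axitinib dose intensity, which events count as on-treatment, and which deaths count as close to the last dose.

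**Working it through.** The plan gives no figure to reproduce, so the check applies the three branches literally and compares them with the same rule plus an earlier-year condition in branch 2. The dates are illustrative assumptions, not trial data.

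| Recorded last dose | EOT | SAP rule | With added condition | Difference |
|---|---|---|---|---|
| Oct 2018 | 15 Dec 2018 | 31 Oct 2018 | 31 Oct 2018 | 0 days |
| 2018 only | 15 Jan 2019 | 31 Dec 2018 | 31 Dec 2018 | 0 days |
| Dec 2018 | 5 Jan 2019 | 5 Jan 2019 | 31 Dec 2018 | 5 days |
| Oct 2018 | 15 Jan 2019 | 15 Jan 2019 | 31 Oct 2018 | 76 days |
| Oct 2018 | 15 Mar 2019 | 15 Mar 2019 | 31 Oct 2018 | 135 days |

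The first two rows show that the existing branches work where they apply. The second and fourth rows share an EOT date: knowing the month moves the imputed date from 31 December 2018 to 15 January 2019.

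The fourth row carried into the analyses:

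- **On-treatment window** (last dose + 30 days, no new drug therapy first): ends 14 February 2019 instead of 30 November 2018.
- **irAE window** (last dose + 90 days): ends 15 April 2019 instead of 29 January 2019.
- **30-day deaths.** If the patient died on 15 January 2019 with no earlier EOT date, last dose is set to the death date. The gap is 0 days and the death is counted. With the added condition the gap is 76 days and it is not.
- **Axitinib** (SAP 6.5.3.2). Assume a first dose on 1 February 2018 and 10 mg/day through 31 October 2018: 273 days and 2,730 mg. Exposure is 273/7 = 39.0 weeks, and RDI is 100 × 2,730/(7 × 2 × 5 × 39.0) = 100%. Under the SAP rule exposure runs to 15 January 2019: 273 + 76 = 349 days, or 349/7 = 49.9 weeks. RDI becomes 100 × 2,730/(70 × 349/7) = 100 × 2,730/3,490 = 78.2%.

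Overall dose intensity for avelumab and sunitinib is based on the start of the last dosed cycle (SAP 6.5.3.1, 6.5.3.3). For those drugs it is mainly the duration of exposure that changes.

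**The case against.** The gap itself is plain on the text, and no other section repairs it. The case on the other side concerns its reach, and most of that stands.

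- **A reader might infer that every adverse event up to death becomes treatment-emergent.** The documents do not support this. The window stops the day before new anti-cancer drug therapy (SAP 5.2.7). In Arm A it moves only if the imputed date becomes the later of the two drugs' last doses (SAP 3.4.1). Routine AE recording ends 90 days after the last administration, and sooner for nonserious events if new therapy starts (Protocol 8.2). In the October example that is no later than 29 January 2019 (31 October + 90 days), so the later part of an extended window has few events to collect.
- **A reader might infer that primary PFS is biased.** Last dose enters SAP 5.3.3.4 only when the start date of new therapy is itself missing or partial. Even then it sits inside a maximum with PD date + 1 and a minimum with the therapy end date. PFS is censored at the last adequate assessment (SAP 6.1.1.1), so a shifted start matters only if an assessment or event falls in between. The primary PFS and OS definitions do not use last dose.
- **The automatic 30-day death needs an absent EOT date or one no earlier than death.** The protocol schedules an EOT visit and lists death among the reasons for stopping treatment (Protocol 6.5), so an EOT record is expected. If it precedes death, the minimum returns the EOT date.
- **Frequency is not documented.** Diaries and bottle returns every 6 weeks (Protocol 5.2) limit missing days for the oral drugs, and avelumab is given at the site. Imputed values are flagged in listings (SAP 5.3.1).

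One objection does not stand: that the differences are measured from another imputed date. Month end is the latest day consistent with the record, so each difference is a lower bound. For October 2018 with EOT on 15 January 2019, the SAP date is at least 76 and at most 106 days late (76 + 30, if the last dose was on 1 October).

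**Conclusion.** The concern holds as a minor drafting error. Read literally, SAP 5.3.2.4 gives a last-dose date that contradicts the recorded month when the day is missing, the month is known, and the recorded year is earlier than that of the earlier of EOT and death.

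For those patients it lengthens drug-level exposure and lowers axitinib RDI. The effects on the on-treatment window, the irAE window and the 30-day death count are conditional, as set out above. The shift depends on the gap from the recorded month to EOT or death: a few days to some months in the illustrations, with 135 days at the long end and not to be taken as typical. The number of patients is not given and is probably small. No hypothesis test, boundary or primary endpoint definition depends directly on the rule.

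It is still worth correcting. A program that follows the text imputes a date the record rules out, and a program that avoids this departs from the SAP.

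**What to change.** In SAP 5.3.2.4, widen the second branch. When year and month are both known, use the last day of that month if either (a) the recorded year is earlier than the year of min(EOT, death), or (b) the years are equal and the recorded month is earlier than the month of min(EOT, death). This is the logic already used in SAP 5.3.3.4.

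Leave the third branch unchanged. It is still needed for a year-only date in the same year as min(EOT, death), for a recorded month equal to or later than that of min(EOT, death), and for a date that is wholly missing. Narrowing it would leave some of these with no rule.

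The cost is one line of SAP text and one condition in the derivation program, with no new data.

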5.3.3. Imputation rules for date of last contact and efficacy assessments

5.3.3.1. Date of last contact

The date of last contact will be derived for patients not known to have died at the analysis cut-off using the latest complete date among the following:

- All patient assessment dates (blood draws (laboratory, PK), vital signs, performance status, ECG, tumor assessments)
- Start and end dates of anti-cancer therapies administered after study treatment discontinuation
- AE start and end dates
- Last date of contact collected on the 'Survival Follow-up' eCRF (do not use date of survival follow-up assessment unless status is 'alive')
- Study drug start and end dates
- Randomization date
- Withdrawal of consent date
- Date of discontinuation on disposition eCRF pages (do not use if reason for discontinuation is lost to follow-up).

Only dates associated with actual examinations of the patient will be used in the derivation. Dates associated with a technical operation unrelated to patient status such as the date a blood sample was processed will not be used. Assessment dates after the cut-off date will not be applied to derive the last contact date.

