17. **Survival Assessment:** All patients will be followed for survival and subsequent anticancer therapies every 3 months ( $\pm 14$  days) until death, end of the study or patient withdrawal of consent, whichever comes first. Information will be collected by telephone call unless the patient is visiting the site for other reasons. The Sponsor will request an "ad hoc" survival update prior to each protocol-specified interim analysis and final analysis. The investigator or designee must make every effort to collect the patient's status through contacting the patient or a relative or their usual health care provider by telephone or other allowed methods. These contact attempts should be documented in the patient's medical record.
18. **Patient-Reported Outcome Questionnaire:** FKSI-19 and EUROQoL 5-Dimension (EQ-5D) are to be administered at the End of Treatment/Withdrawal visit. PROs should be administered prior to other End of Treatment/Withdrawal measures. Beyond End of Treatment (ie, follow-up period), PRO assessments will be collected at the same time a tumor assessment is performed.
19. **Pharmacokinetics:** In Arm A, PK blood samples for avelumab (3.5 mL) will be taken 1 month after end of avelumab treatment. Details are outlined in Section 7.3.
- [REDACTED]
21. **De Novo Tumor Biopsy:** A *de novo* (ie, fresh biopsy) tumor sample should also be collected at End of Treatment/Withdrawal visit, unless clinically contraindicated. Tumor tissue from cytologic sampling (eg, fine needle aspiration, including FFPE cell pellet material), is not adequate and should not be submitted. The *de novo* biopsy(ies) should be formalin-fixed and paraffin-embedded as per routine (see Study Manual), [REDACTED] should be submitted to the Central Laboratory. See [Section 7.5.1](#).
22. **Anti-Avelumab Antibodies (Anti-Drug Antibodies, ADAs) and Neutralizing Antibodies (Nab):** In Arm A, one blood sample (3.5 mL) for anti-avelumab antibodies (and simultaneous pharmacokinetic draws for measurement of avelumab) will be collected at 30 days after the end of avelumab treatment. All the samples that are positive for ADA may also undergo characterization for Nab. See [Section 7.4](#).
23. **MUGA Scan or ECHO.** For the evaluation of the left ventricular ejection fraction, the technique used at screening will be consistently used throughout the study, in the following assessments.

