2. INTRODUCTION

This SAP provides the detailed methodology for summary and statistical analyses of the data collected in study B9991003. This document may modify the plans outlined in the protocol; however, any major modifications of the primary endpoint definition or its analysis will also be reflected in a protocol amendment.

CCI

Statistical analyses will be performed using cleaned eCRF data as well as non-CRF data (i.e., tumor assessment results by the Blinded Independent Central Review (BICR), PK concentration, Anti-Drug Antibody (ADA), Neutralizing Antibody (nAb), biomarker data).

The primary analysis for progression-free survival (PFS) will include all data up to a cut-off date which is determined by the number of events required for the primary analysis of PFS in PD-L1 positive patients and a minimum follow-up of 12 months after the last patient is randomized.

The primary analysis for overall survival (OS) will include all data up to a cut-off date which is determined by the number of events required for the primary analysis of OS in PD-L1 positive patients.

The cut-off dates are determined once a data extract (before database lock) is available which indicates that the required number of events for PFS by Blinded Independent Central Review (BICR) assessment in PD-L1 positive patients and the minimum follow-up of 12 months, or the required number of events for OS in PD-L1 positive patients have occurred.

Due to data cleaning activities, the final number of events might deviate from the planned number. The data cut-off date will not be adjusted retrospectively in this case.

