5.2.1. Data handling after the cut-off date

Data after the cut-off date may not undergo the cleaning process and will not be displayed in any listings or used for summary statistics, statistical analyses or imputations.

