6.1.2. Overall survival in PD-L1 positive patients

6.1.2.1. Primary analysis

The following analyses will be based on the FAS using the strata assigned at randomization.

Overall survival (OS) is defined as the time from date of randomization to the date of death due to any cause. Patients last known to be alive will be censored at date of last contact.

$$\text{OS (months)} = [\text{date of death or censoring} - \text{date of randomization} + 1] / 30.4375$$

The primary analysis of OS will compare the OS time between the experimental arm and the control arm, and will be performed using a 1-sided stratified log-rank test as described in Section 5.1.

The treatment effect will be estimated using a Cox's Proportional Hazard model stratified by the randomization strata to calculate the hazard ratio. Each stratum will define a separate baseline hazard function (using the 'STRATA' statement in SAS PROC PHREG), i.e. for the i -th stratum the hazard function is expressed as: $h(i;t) = h(i,0;t) \exp(x\beta)$, where $h(i,0;t)$ defines the baseline hazard function for the i -th stratum and x defines the treatment arm (0=control arm, 1= experimental arm) and β is the unknown regression parameter.

Ties will be handled by replacing the proportional hazards model by the discrete logistic model (Ties=Discrete option in SAS PROC PHREG).

In order to account for the group sequential design in this study, the repeated CI (RCI) method, will be used to construct the 2-sided RCIs for the hazard ratio at the interim and the final analyses of OS. In addition, the unadjusted 95% CIs for the hazard ratio will also be reported at the interim and the final analyses for OS.

Kaplan-Meier estimates (product-limit estimates) will be presented by treatment arm together with a summary of associated statistics including the median OS time with 2-sided 95% CIs. In particular, the OS rate at 6, 12, 18, 24, 30, 36, 42, 48, 60 months will be estimated with corresponding two-sided 95% CIs. The CIs for the median will be calculated according to [Brookmeyer and Crowley](#) and the CIs for the survival function estimates at the time points defined above will be derived using the log-log transformation according to [Kalbfleisch and Prentice](#) (conftype=loglog default option in SAS Proc LIFETEST) with back transformation to a CI on the untransformed scale. The estimate of the standard error will be computed using Greenwood's formula.

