Frequency (number and percentage) of patients with an event (death) and censoring reasons will be presented by treatment arm. Reasons for censoring will be summarized according to the categories in Table 11 following the hierarchy shown.

Table 11. OS Censoring Reasons and Hierarchy

Hierarchy	Condition	Censoring Reason
1	No event and [withdrawal of consent date \geq date of randomization OR End of study (EOS) = Subject refused further follow-up]	Withdrawal of consent
2	No event and [lost to follow-up in any disposition page OR data cut-off date – last contact date > 16 weeks]	Lost to follow-up
3	No event and none of the conditions in the prior hierarchy are met	Alive

The OS time or censoring time and the reasons for censoring will also be presented in a patient listing.

Time of Follow-Up for OS

A Kaplan-Meier plot for OS follow-up duration will also be generated to assess the follow-up time in the treatment arms reversing the OS censoring and event indicators. Kaplan-Meier estimates (product-limit estimates) will be presented by treatment arm together with a summary of associated statistics including the median time of follow-up for OS with 2-sided 95% CIs. In particular, the rate at 6, 12, 18, 24, 30, 36, 42, 48, 60 months will be estimated with corresponding 2-sided 95% CIs.

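### SAP 5.3.3.1 ignores proof of survival dated after the cut-off while deaths up to the cut-off count, so interim landmark OS can be about 2 to 3 points too low; the rule has no direction of its own on the hazard ratio

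*SAP*

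**What the plan says.** - SAP 6.1.2.1 (OS primary analysis): "Patients last known to be alive will be censored at date of last contact".
- SAP 5.3.3.1 says who gets such a date: "The date of last contact will be derived for patients not known to have died at the analysis cut-off". It takes the latest complete date from a list of patient contacts and closes with: "Assessment dates after the cut-off date will not be applied to derive the last contact date".
- SAP 5.2.1: data after the cut-off may be uncleaned and "will not be displayed in any listings or used for summary statistics, statistical analyses or imputations".
- SAP 2, on the primary PFS and OS analyses: "The cut-off dates are determined once a data extract (before database lock) is available". The cut-off is not moved if data cleaning later changes the event count.
- Protocol, Schedule of Activities for the post-treatment period, footnote 17: survival contact is every 3 months (±14 days) in both arms, and the sponsor requests an ad hoc "survival update prior to each protocol-specified interim analysis and final analysis". Footnote 21 of the post-IA3 schedule repeats this. Neither document says whether that update falls before or after the cut-off.
- SAP Table 11 labels a patient without an event as lost to follow-up if there is "lost to follow-up in any disposition page" or if more than 16 weeks separate last contact from the cut-off.

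**The concern.** Suppose a status call is made after the cut-off. Under these rules its effect depends on the answer:

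| Call finds | Effect on OS |
|---|---|
| Died on or before the cut-off | Event on the date of death |
| Died after the cut-off | Call unused; censored at an older contact |
| Alive | Call unused; censored at an older contact |

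In the last two rows the patient is known to have survived to the cut-off, yet that event-free time is dropped. In the final contact interval the risk set therefore loses survivors but keeps deaths, and the right-hand end of the Kaplan-Meier curve is pulled down.

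OS in PD-L1 positive patients is a primary endpoint with four looks, and SAP 6.1.2.1 reports medians and landmark rates from 6 to 60 months. A landmark close to the end of follow-up is where the loss shows most.

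**Working it through.** **1. The plan's own figure.** With HR 0.70, 1-sided alpha 0.021 and 90% power (SAP 5.1.1), the fixed-design count is 4(z₀.₀₂₁ + z₀.₁₀)² / (ln 0.70)² = 4 × (2.0335 + 1.2816)² / 0.1272 = 346 deaths. Simulating the four-look design with 368 deaths and the SAP Table 5 boundaries gives power of 90.0% with futility stops obeyed and 91.2% with them ignored. SAP Table 8 shows 0.8943. The stated design is reproduced.

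**2. How old a contact can be.** Off treatment: 3 × 30.4375 + 14 = 105 days. On treatment, contacts are about 2 weeks apart in both arms up to IA3 (Arm B has Day 15 and Day 29 laboratory draws). After IA3, Arm A keeps 2-weekly infusions and Arm B comes about every 6 weeks.

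**3. Model.** From the documents: 580 PD-L1 positive patients, 1:1, 21-month accrual, control median OS 26.4 months, median PFS 11 and 16.9 months. Assumed: ramp-up accrual, exponential OS and time on treatment (PFS medians as proxy), last contact uniformly 0 to 14 days old on treatment and 0 to 3 months old off treatment, no update before the cut-off. Under HR 0.70 this gives 123/188/293/372 deaths at months 25/32/46/61, against 125/195/294/368 planned. Survivors censored at the cut-off are compared with survivors censored at the last earlier contact.

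**4. OS level, true HR 0.70.**

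| Arm B landmark | Censored at cut-off | SAP rule | Difference |
|---|---|---|---|
| 18 months at IA1 | 0.627 | 0.593 | −3.4 points |
| 24 months at IA2 | 0.532 | 0.500 | −3.2 points |
| 36 months at IA3 | 0.388 | 0.366 | −2.2 points |

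Arm A falls by about 2 points at the same times. The crude death rate is overstated by 6 to 7% at IA1, 2.6% at IA3 and 1.5 to 1.7% at the final analysis. A median near the end of follow-up can drop by more than a month (Arm B at IA2 by 1.7, Arm A at IA3 by 1.5). At the final analysis it moves by less than 0.05 month.

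**5. Hazard ratio under the SAP rule divided by hazard ratio with censoring at the cut-off.**

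| Contact pattern | IA1 | IA2 | IA3 | Final |
|---|---|---|---|---|
| Planned schedule, no update, HR 0.70 | 0.986–0.987 | 0.991 | 0.996 | 0.998 |
| Same, no OS effect, planned PFS difference | 0.985 | 0.989 | 0.995 | 0.997 |
| Gaps 0–105 days in both arms | 1.0015 | | | 1.0001 |
| Arm A 0–14 days, Arm B 0–105 days (extreme) | 0.870 | | | 0.980 |
| The reverse (extreme) | 1.149 | | | 1.021 |

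An update 0 to 28 days before the cut-off in both arms gives 1.0000 to 1.0002 at every look.

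**6. On the test scale.** The shift in z is about −ln(ratio) × √d / 2. IA1: −ln(0.987) × √125 / 2 = 0.07, against a boundary of −3.7913. Final: −ln(0.6984/0.6995) × √368 / 2 = 0.015, against −2.0975. With no OS effect but the planned PFS difference, the rejection rate is 0.022 with censoring at the cut-off and 0.024 under the SAP rule (standard error about 0.002).

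**7. What an earlier update does to the level.** In that same no-OS-effect scenario, the 28-day update lowers the overstatement of the crude death rate at IA1 from 6.1% (Arm A) and 7.6% (Arm B) to 4.6% in each arm. At the final analysis it falls from 1.8% and 2.0% to 0.7%. The update therefore removes the hazard-ratio shift at once, but removes the level bias only as it closes in on the cut-off.

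**8. Table 11.** Two in-window contacts can be 91 + 14 + 14 = 119 days apart, which is 17 weeks and beyond the 16-week limit.

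**The case against.** A reader might infer that this rule in itself pushes the OS hazard ratio towards Arm A and inflates the type I error. The documents do not support that. No section gives the arms different censoring rules, and both arms have the same 3-monthly survival contact and the same ad hoc update. Equal gaps leave the hazard ratio unchanged, and reversing the gaps reverses the sign. The extreme gaps in step 5 would move the 1-sided error to 0.040, or to 0.008 if reversed, but nothing in the plan implies them.

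The no-update case is also a worst case that no section states:

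- IA3 is fixed by calendar, 15 months after the primary PFS analysis, so its update can be timed in advance.
- The model omits planned contacts: the 30, 60 and 90-day visits, scans that continue until BICR-confirmed progression, and subsequent-therapy dates. Adding only the 30/60/90-day visits cuts the IA1 shift in z under HR 1 from 0.085 to 0.060; later looks barely change.
- Treatment may continue beyond progression, so the PFS medians may understate time on treatment.

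The Table 11 label changes no OS time, event or test. And SAP 5.2.1 warns that post-cut-off data may be uncleaned, so an edit to 5.3.3.1 alone would contradict it.

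All of this stands, and it limits the point to the OS level and to an unstated date. It does not remove the point: nothing in either document ensures that the update precedes the cut-off.

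**Conclusion.** The concern holds in a limited form. As written, the SAP censors OS too early for every survivor confirmed alive only after the cut-off. If no update precedes the cut-off, interim landmark rates near the end of follow-up are about 2 to 3 points low in each arm. At the final analysis the effect on the median and the hazard ratio is negligible.

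The rule has no direction on the hazard ratio. A shift towards Arm A needs longer contact gaps in Arm B. The planned PFS medians, and the thinner Arm B visit schedule after IA3, make that plausible but not certain. The size would then be about 1.5% at IA1 and 0.2 to 0.3% at the final analysis. The accompanying difference in rejection rate is no larger than the simulation error.

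The sizes rest on the assumed accrual shape, time on treatment and uniform gaps. The asymmetry itself rests on reading SAP 5.3.3.1 by date of death rather than by date of report. SAP 2 fits that reading, since it expects cleaning to change the event count at a fixed cut-off.

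**What to change.** - **SAP 5.3.3.1:** if any record shows the patient alive on or after the cut-off, or dead after it, set the last-contact date to the cut-off date and censor OS there. Apply the same date to the PFS2 rows in Table 14 that are censored at last contact.
- **SAP 5.2.1:** add an exception limited to vital-status dates.
- **SAP Table 11:** do not apply the 16-week lost-to-follow-up label to these patients. This is descriptive only.
- **Useful addition:** report the gap from last contact to cut-off by arm at each look, so that any imbalance is visible.

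The SAP already uses the cut-off date in this way for ongoing patients, in 5.3.2.4 (last dose) and 5.3.3.4 (imputed start of new therapy). The cost is a few sentences and one derivation step. The ad hoc update already collects the data. The downside is that the post-cut-off vital-status dates must be checked before database lock.
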